# 7.3 Laboratory tests

Local laboratory data will only be listed on the SCR as data is only included in the eCRF in case the investigator decides to collect the local lab data.

# 7.4 Vital signs, blood pressure and pulse rate

The change from baseline to Week 4 in vital signs (systolic and diastolic blood pressure, and pulse rate) will be summarized based on the FAS by treatment. The observed values at baseline and each scheduled post-baseline visit will also be summarized for the FAS.

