Daridorexant (ACT-541468) Insomnia and comorbid nocturia Protocol ID-078A401 Version 3

4 September 2023, page 44/122

Objectives	Endpoints in period I and period II			
	• Changes from baseline to Week 1, Week 2, Week 3, and Week 4 in Patient Global Impression of Change (daytime and nighttime symptoms)			
	 Change from baseline to Week 4 in Patient Global Assessment of Disease Severity (daily life) Change from baseline to Week 4 in Patient Global Impression of Change (daily life) 			
	• Change from baseline to Week 2 and Week 4 in EQ-5D-3L score			
	• Treatment satisfaction at Week 4 assessed via NRS			
	• Treatment period preference at Visit 8 (EOTP II)			
To explore a) the sensitivity of the IDSIQ to detect clinical changes in this study population and b) the use of narratives to report subject's perception of treatment effect	 The change from baseline to Week 1, Week 2, Week 3, and Week 4 in all IDSIQ domains The subjects will be asked to complete a narrative at the end of each treatment period. More details on the analysis will be provided in the SAP. 			
To assess the safety and tolerability of daridorexant	Safety endpoints			
	Safety monitoring will include:			
	• Occurrence of TEAEs up to 5 days after EOTP I and/or EOTP II.			
	• Occurrence of treatment emergent AESIs up to 5 days after EOTP I and/or EOTP II.			
	• Occurrence of treatment-emergent serious adverse events up to 5 days after EOTP I and/or EOTP II.			
	Occurrence of TEAEs leading to premature discontinuation of the study and/or treatment.			
	• Change from baseline to EOTP I and EOTP II in vital signs (systolic blood pressure, diastolic blood pressure, and pulse rate).			
	• Change from baseline to EOTP I and EOTP II in morning sleepiness as determined by the scores on the VAS in the morning.			
	• Occurrence of suicidal ideation, suicidal behavior, and/or self-injurious behavior with / without suicidal intent based on the C-SSRS [©] at Visit 1, Visit 4, Visit 5, Visit 8, and Visit 9.			

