9.1.7 Usage of the analysis sets

The analyses of the primary endpoint and all exploratory efficacy endpoints will be performed using the FAS. Baseline and disease characteristics will be analyzed on the FAS as well.

The analyses of the primary endpoint will be repeated based on the PPS.

The Safety set will be used for the analysis of safety endpoints (including previous and concomitant medications, and study treatment exposure).

Subject data will be listed using the SCR, unless otherwise specified.

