9.2.5 Analysis of safety outcomes

The Safety set will be used to perform all safety analyses. Safety analyses will be conducted by period.

If not otherwise stated, only treatment-emergent safety data will be considered in tables and figures. All safety data will be included in listings, with flags for safety data not considered to be treatment emergent.

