# 4.3 Usage of the analysis sets

The analyses of the primary endpoint and all other efficacy endpoints will be performed using the FAS.

The analyses of the primary endpoint will be repeated based on the PPS.

The SAF will be used for the analysis of safety endpoints (including previous and concomitant medications, and study treatment exposure).

The SCR is used to provide the same summaries for the screen failures.

Subject disposition will be described based on the SCR.

Study subjects' data will be listed using the SCR, unless otherwise specified.

Of note, there are no baseline disease characteristics collected in this study other than baseline values of efficacy and safety variables.

Table 2 Usage of analysis datasets

Analysis	SCR	RND	FAS	PPS	SAF
Subject disposition	X				
Demographics / Baseline Characteristics		X*	X*		
Previous and concomitant medication					X
Study drug exposure					X
Efficacy analysis			X	X	
Safety and tolerability analyses					X

FAS = full analysis set; PPS = per-protocol analysis set; RND = randomized analysis set; SAF = safety analysis set; SCR = screened analysis set.

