# **6.3.1** Analysis of insomnia-related endpoints (ISI®, VAS, number of awakenings) All endpoints will be summarized based on the FAS.

# 6.3.1.1 Insomnia Severity Index©

The ISI© assesses the severity of a subject's insomnia by scoring the severity of sleep onset and sleep maintenance difficulties and any insomnia-related interference with daytime functioning. The assessment is on a 5-point scale (0–4) where the composite score is obtained by summing the 7 rated dimensions measuring the subject's perception of his or her insomnia. The ISI© will be completed by the subject on the eDiary at Visit 1 (baseline), Visit 3 (Week 2, Period 1), Visit 4 (Week 4, Period 1), Visit 7 (Week 2, Period 2), and Visit 8 (Week 4, Period 2).

The change from baseline to Week 2 and Week 4 will be summarized by treatment. Observed values will also be summarized. Changes from baseline to Week 2 and Week 4 will also be analyzed based on an MMRM, as described in Section 6.1.3.

In addition, the proportion of subjects with an ISI© decrease from baseline of greater than or equal to 6 will be summarized, as well as the proportion of subjects with ISI© values of 7 or less at Week 2 and Week 4, by treatment.

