# 7.6 Morning sleepiness (VAS)

Morning sleepiness is analyzed as described in Section 6.3.1.2.

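### SAP 7.4 puts vital signs, a safety endpoint, on the FAS by assigned treatment, where the protocol and SAP 4.3 call for the Safety set by treatment received

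*SAP*

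**What the plan says.** Protocol 3.4, Table 3, lists this among the safety endpoints: "Change from baseline to EOTP I and EOTP II in vital signs (systolic blood pressure, diastolic blood pressure, and pulse rate"). Protocol 9.2.5 then gives a rule without exceptions: "The Safety set will be used to perform all safety analyses". Protocol 9.1.7 assigns safety endpoints to the same set, and 9.1.5 has subjects in it analysed by the treatment they received in each period.

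The SAP repeats this in its section on analysis sets. SAP 4.3 reads "The SAF will be used for the analysis of safety endpoints (including previous and concomitant medications, and study treatment exposure"), and the Table 2 row for safety and tolerability is marked under the SAF only. SAP 4.1.5 uses treatment received per period. SAP 7.1 makes the SAF the default for safety tables and listings, but leaves room for another set where one is stated.

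SAP 7.4 names another set twice. The change from baseline to Week 4 "will be summarized based on the FAS by treatment", and "The observed values at baseline and each scheduled post-baseline visit will also be summarized for the FAS". Under SAP 4.1.3 the FAS evaluates subjects by assigned treatment, and that section notes that this may differ from the treatment received.

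For morning sleepiness, also a protocol safety endpoint, SAP 7.6 says only: "Morning sleepiness is analyzed as described in Section 6.3.1.2".

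**The concern.** The two analysis sets exist side by side because they attribute data differently. For safety, the usual question is what happened to subjects on the drug that they actually took. Under SAP 7.4, a subject who took the wrong drug in a period would have blood pressure and pulse from that period reported under the drug not taken, while the same subject's adverse events would be reported under the drug taken. In a cross-over, a subject whose two periods were swapped puts on-drug values in the placebo column and placebo values in the daridorexant column. Such misattribution pulls the two columns together, so it dilutes a true safety difference.

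A dispensing error is not far-fetched: SAP 4.1.4 lists, under PD code 02A01, a wrong blister from which at least one tablet was taken. That deviation removes the subject from the PPS but not from the FAS.

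**Working it through.** The plan gives no figure to reproduce. The check compares the rules and then sizes the consequence.

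**1. Rules side by side**

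| Place | Set for vital signs | Attribution |
|---|---|---|
| Protocol 9.1.7 and 9.2.5 | Safety set | Received, per period (9.1.5) |
| SAP 4.3 and Table 2 | SAF | Received, per period (4.1.5) |
| SAP 7.1 | SAF by default, exceptions allowed | Received, per period |
| SAP 7.4, both sentences | FAS | Assigned (4.1.3) |

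**2. Is the departure declared?** SAP 11.1 reports no changes to the protocol's analyses. SAP 11.3 mentions in general terms that some outputs are repeated on another population. SAP 7.4 is not a repeat, because no SAF version of the vital signs summary is planned.

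**3. Do the sets differ in membership?** The FAS is randomized subjects with at least one dose. The SAF is subjects with at least one dose. Study drug is given only after randomization, so the members are in effect the same. Only the column in which a value is counted can differ.

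**4. Size.** Assumptions, for illustration: n = 50 (the approximate planned number in SAP 2), both periods observed in everyone, and a common mean treatment difference d by treatment received, with period effects ignored.

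- *Both periods swapped in m subjects.* Each such subject contributes −d to the by-assigned comparison and every other subject +d. The by-assigned difference is [(n − m)d − md]/n = d(1 − 2m/n).
  - m = 1: 1 − 2/50 = 0.96, a shrinkage of 4%.
  - m = 2: 1 − 4/50 = 0.92, a shrinkage of 8%.
  - m = 5: 1 − 10/50 = 0.80, a shrinkage of 20%.
- *Wrong drug in one period only in m subjects.* Each such subject took the same drug twice and contributes 0. The by-assigned difference is about d(1 − m/n). For m = 1 this is 1 − 1/50 = 0.98, a shrinkage of about 2%.
- *No misdosing (m = 0).* The factor is 1 and the FAS and SAF tables agree.

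**5. Morning sleepiness.** SAP 7.6 refers to 6.3.1.2, which defines the VAS variables and analysis but names no set. The parent section, 6.3.1, says "All endpoints will be summarized based on the FAS", under a heading about insomnia endpoints. SAP 11.4 adds MMRM analyses of VAS scales on the FAS, without saying whether morning sleepiness is among them. The opening of SAP 6 ties the FAS to efficacy endpoints, and the 7.1 default for safety data is the SAF. Both readings are open.

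**The case against.** The best defence is the exception clause in SAP 7.1: section 7.4 states another set, so within Section 7 it is a permitted exception and not a contradiction. That stands as far as it goes. It does not reconcile 7.4 with SAP 4.3 and Table 2, and an SAP clause cannot override the protocol's rule, which has no such exception. No reason for an exception is given.

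It can also be said that little depends on the choice. The sets have the same members, the vital signs summaries are descriptive with no test, safety data are listed by subject, and protocol deviations are summarized and listed, so a mix-up would be visible. All of that stands, and it limits the importance of the point.

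Two stronger readings are tempting, and the documents do not support them.

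- A reader might infer that morning sleepiness is also placed on the FAS, so that two safety endpoints are affected. The cross-reference goes to a subsection that names no set, and the 7.1 default points to the SAF. The text shows ambiguity only.
- A reader might infer from PD code 02A01 that swapped treatment is expected. The code makes it possible but does not establish it. A wrong blister may hold the same treatment, a single tablet is not a whole period, and Week 4 vital signs might not be affected at all. The documents give no misdosing rate.

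**Conclusion.** The point holds for vital signs. SAP 7.4 uses a set and an attribution rule that conflict with the protocol and with SAP 4.3 and Table 2, and the departure is not declared. For morning sleepiness the finding is only that the analysis set is unclear.

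The consequence is narrow. It is nil unless someone received a drug other than the one assigned. Under the assumptions above, it is a dilution of about 4% per fully swapped subject and about 2% per one-period error; partial exposure to the wrong drug would be expected to do less. It does not touch the primary analysis. This is a minor correction, worth making because it costs almost nothing and puts vital signs under the same attribution rule as adverse events.

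**What to change.** In SAP 7.4, replace FAS with SAF in both sentences. In SAP 7.6, add: *based on the SAF, by treatment received*. If the FAS was intended for vital signs, the alternative is to keep it and then declare and justify the departure from the protocol in SAP 11.1.

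The cost is one word changed twice and one short phrase added, plus the matching set label in the affected table shells and programs. No new data are needed.

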# 7.5 Columbia Suicide Severity Rating Scale©

The C-SSRS© evaluates suicidal ideation and behaviors.

The C-SSRS© outcome categories are provided below. Each category has a binary response (yes/no).

1 Wish to be dead

Page 36/50

- 2 Non-specific active suicidal thoughts
- 3 Active suicidal ideation with any methods (not plan) without intent to act
- 4 Active suicidal ideation with some intent to act, without specific plan
- 5 Active suicidal ideation with specific plan and intent
- 6 Preparatory acts or behavior
- 7 Aborted attempt
- 8 Interrupted attempt
- 9 Actual attempt (non-fatal)
- 10 Completed suicide

Categories 1–5 relate to suicidal ideation and a score of 0 is assigned if no suicidal ideation is present. Categories 6–10 relate to suicidal behavior.

Self-injurious behavior without suicidal intent is also a C-SSRS© outcome (although not suicide-related) and has a binary response (yes/no).

C-SSRS© data are collected at baseline, at Week 4 (in each treatment period), during the safety follow-up periods, and for premature treatment discontinuation.

Based on the C-SSRS©, the number (%) of study subjects with suicidal ideation by category, suicidal behavior by category, suicidal ideation or suicidal behavior, and/or self-injurious behavior without suicidal intent will be tabulated by study phase. The worst C-SSRS© outcomes of Study Phase 1 (TP I; premature treatment discontinuation during TP I; and washout phase) will be derived, as well as the worst C-SSRS© outcomes of study phase 2 (TP II; premature treatment discontinuation during TP II; and safety follow-up phase). Percentages will be based on the number of study subjects with at least one post-baseline C-SSRS© assessment.

Shifts from baseline showing any change in suicidal ideation and suicidal behavior during the two study phases will be provided by treatment. Study subjects will be summarized under the worst of the following 3 categories, shown here in order from best to worst: 1) No suicidal ideation or behavior, 2) Suicidal ideation, and 3) Suicidal behavior (subjects with both suicidal ideation and suicidal behavior are also included in the suicidal behavior category).

# 7.6 Morning sleepiness (VAS)

Morning sleepiness is analyzed as described in Section 6.3.1.2.

## 7.7 Analysis of narratives

The analyses of the subject narratives will be conducted based on a separate statistical analysis plan.

### 8 GENERAL STATISTICAL METHODOLOGY

## 8.1 General rules for data presentations

Data are listed and summarized as described below.

By-treatment tables will have the following header structure (label and order):

Daridorexant 50 mg	Placebo
N = xxx	N = xxx

where N indicates the total number of subjects randomized to the respective treatment or treated with the respective treatment within the analysis set.

If the treatment sequence is displayed, the header structure will be:

Daridorexant 50 mg / Placebo	Placebo / Daridorexant 50 mg
N = xxx	N = xxx

where N indicates the total number of subjects randomized to the respective treatment sequence within the analysis set, unless otherwise specified.

All listings will be sorted by randomized treatment sequence received, subject number (ascending) and, when appropriate, by visit / date of assessment (ascending). Listings related to the SCR will present a treatment label 'screening failure' to indicate study subjects who were not randomized and will be listed after the study subjects who were randomized or received study treatment, as relevant.

Unless noted otherwise, the following descriptive statistics will be used to summarize data: number (%) of study subjects for categorical variables; descriptive statistics (number of non-missing values, mean, standard deviation, median, Q1, Q3, minimum, maximum) for continuous variables.

## 8.2 Handling of missing dates

An incomplete date (day or month missing), or missing concomitant therapy / AE date, will be imputed as described in Table 6. The 'lower limit' and 'upper limit' refer to the earliest and latest possible dates, respectively.

For example, if concomitant therapy start date / AE onset date is MAR2021 (day missing), the lower limit is 01MAR2021 and the upper limit is 31MAR2021; if concomitant therapy start date / AE onset date is 2021 (day and month missing), the lower limit is 01JAN2021 and the upper limit is 31DEC2021.

Page 38/50

Statistical Analysis Plan for Clinical Study Report Version 2 Doc No D-24.149

Table 6 Imputation rules for an incomplete or missing concomitant therapy or AE date

Field	Incomplete date	Missing date
Concomitant therapy end date / AE resolution date	The upper limit.	No imputation. The therapy / AE is considered as ongoing.
Concomitant therapy start date / AE onset date	The rules below apply in the order presented:  1. If the (imputed) concomitant therapy / AE end date is on or after the start of study treatment, and if the study treatment start falls within the upper and lower limits (inclusive), the study treatment start date of the corresponding treatment period is used.*	Whichever is the earlier of the concomitant therapy end date or study treatment start date.  If the start date is missing the AE will be assigned to both treatment periods.
	2. If the concomitant therapy end date / AE resolution date is missing, and if the study treatment start falls within the upper and lower limits (inclusive), the study treatment start date of the corresponding treatment period is used. # 3. In all the other cases, the lower limit is used.	

\* If both treatment start dates (i.e., those for TP I and TP II) are within the lower and upper limit, the concomitant therapy / AE is duplicated and assigned to both treatment periods, i.e., once with treatment 1 start date and once with treatment 2 start date.)

AE = adverse event; TP = treatment period.

The purpose of imputing concomitant therapy / AE dates is only to assign a concomitant therapy / AE to a specific study period for the summary tables. No imputed date is considered in the medical evaluation of an AE or of a causal relationship between a concomitant therapy and an individual AE.

### 9 INTERIM ANALYSES

No interim analysis will be performed.

#### 10 GENERAL DEFINITIONS AND DERIVATIONS

### **10.1** Treatment start and end dates

Study treatment start or end date is the earliest or latest date, respectively, of dose intake recorded on the 'Study Treatment Log' page for the corresponding treatment period.

## 10.2 Study periods

The screening period is defined as the time from the informed consent date until one day before the study treatment start date of TP I, or date of screening failure.

The treatment periods are defined as the time from the day of study treatment start until the day of EOT (Week 4), or, for those who prematurely discontinued study treatment (i.e., those without an EOT date), until the day of study treatment end date.

Provided the subject starts the second treatment, the washout period is defined as the time from one day after the end of TP I until the day before start of TP II.

The safety follow-up period is defined as the time from one day after the end of the last treatment period until end of safety follow-up period / EOS date (for both treatment periods).

## 10.3 Treatment day and Study day

The Treatment day for an assessment or event will be calculated using the study treatment start date of the corresponding treatment period as reference.

For assessments/events occurring on or after the start date of study treatment, Treatment day will be positive and will be calculated as:

Treatment day (days) = Date of assessment/event – Start date of study treatment
 + 1 day

The first day of study treatment is Treatment day 1.

Study day will be calculated as:

• Study day (days) = Date of assessment/event – Start date of study treatment in TP I

For all assessments/events occurring prior to the start date of TP I, Study day will be negative. Study day will be displayed in the data listings as appropriate.

### 10.4 Baseline

Baseline is the last non-missing assessment performed or value measured before or on the day of the first dose of any study treatment, unless otherwise defined in the specific analysis section.

Study subjects with no data for a given parameter before the first treatment administration will have a missing baseline (and missing change from baseline) for this parameter.

## 10.5 Change from baseline

The change from baseline is defined as the post-baseline value (any assessment performed after baseline and up to EOS) minus the baseline value. A positive number indicates an increase compared to baseline.

Page 40/50

Statistical Analysis Plan for Clinical Study Report Version 2 Doc No D-24.149

## 11 CHANGES OR CLARIFICATIONS TO ANALYSES PLANNED IN THE STUDY PROTOCOL

# 11.1 Changes to the analyses planned in the study protocol Not applicable.

# **11.2** Changes in the conduct of the study / data collection Not applicable.

## 11.3 Clarifications concerning endpoint definitions and related variables or statistical methods

Analyses for the key voiding endpoints 'Total nocturnal voiding volume' and 'Total number of nocturnal voids' were updated to address potential inconsistencies in the Minze Health voiding data.

Due to issues involving the weekly PGA and PGI endpoint data collection, a time window approach was introduced. Analyses remain the same.

Some minor clarifications were added for C-SSRS© analyses.

Two of the PDs were updated for the definition of the PPS population.

Generally, some minor clarifications were added to the SAP, e.g. outputs repeated on a different population.

The duration of the safety follow-up period was set to 5 days (instead of the 5–10 days specified in the protocol).

## 11.4 Additional analyses to those planned in the study protocol

Baseline disease characteristics summary tables were added for the RND and FAS.

A table summarizing the duration of the washout period was added.

The study discontinuations summary table will also be produced for the FAS.

Analyses for ISI©, VAS scales and IDSIQ scales will be repeated based on an MMRM for the FAS.

An analysis by treatment period was added for the missing data patterns of the primary endpoint and for the compliance summary table.

Two sensitivity analyses each were added for 'Total nocturnal voiding volume' and 'Total number of nocturnal voids' to account for missing and inconsistent data.

For the time to first nocturnal void, a Kaplan-Meier plot was added for all subjects at baseline.

Daridorexant (ACT-5414	168 )
ID-078A401	
30 May 2024	
Page 41/50	

Confidential

Statistical Analysis Plan for Clinical Study Report Version 2 Doc No D-24.149

An analysis was added for the total nocturnal voiding volume plus the morning void volume.

